8.1.4 Early Discontinuation

Early Termination Visit will be conducted when a subject withdraws or is withdrawn from the study (Section 9.4), or 1 or multiple study sites are closed (Section 13.2.7). Assessments at the Early Termination Visit are listed in Table 3-1. The Safety Follow-up Visit will be required in addition to the Early Termination Visit only for subjects who prematurely terminate from the study prior to Day 28 after treatment. Subjects who prematurely terminate from the study subsequent to Day 28 after treatment will only be required to complete the Early Termination Visit.

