12.3.1 General Considerations

All individual subject data for all individual subjects randomized or received study drug will be presented in data listings.

Continuous variables will be summarized using the following descriptive summary statistics: the number of subjects (n), mean, SD, standard error (SE), median, minimum value (min), and maximum value (max). The precision of the measurement for each continuous variable will be used to determine the number of decimal places to present in tables, figures, and derived listings. Unless otherwise specified, min and max values will be reported with the same precision as the units of measure; the mean, median, SD, and SE will be reported to 1 greater decimal place. Any values that require transformation to standard units (metric or International System [SI]) will be converted with the appropriate corresponding precision. Details will be provided in the SAP.

Categorical variables will be summarized using counts and percentages. Percentages will be presented to 1 decimal place.

Baseline value, unless otherwise specified, will be defined as the most recent non-missing measurement (scheduled or unscheduled) collected before administration of study drug.

Change (absolute change) from baseline will be calculated as postbaseline value - baseline value.

The treatment-emergent (TE) period will include the time from dosing with study drug to the Safety Follow-up Visit or 28 days after treatment for subjects who do not have a Safety Follow-up Visit.

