12.3.4.1 Adverse Events

For analysis purposes, AEs will be classified as pretreatment AEs, TEAEs, or post-treatment AEs, defined as follows:

- Pretreatment AE: Any AE that started prior to dosing with study drug.
- TEAE: Any AE that developed or worsened at or after dosing of study drug through the end of the TE period.
- Post-treatment AE: Any AE that developed or worsened beyond the TE period.

For AEs with missing or partial missing start dates, if there is no clear evidence that the AEs started before or after study treatment, then the AEs will be classified as TEAEs.

AE summary tables will be presented for TEAEs only and will include the following:

- All TEAEs
- TEAEs by relationship
- TEAEs by maximal severity
- Serious TEAEs
- TEAEs leading to death

Summaries will be presented by MedDRA system organ class and preferred term using frequency counts and percentages (i.e., number and percentage of subjects with an event as well as total number of events). When summarizing the number and percentage of subjects with an event, subjects with multiple occurrences of the same AE or a continuing AE will be

counted once, only the maximum severity level will be presented in the severity summaries, and the worst/highest relationship level in the relationship summaries. An AE overview table will be provided. A separate table will summarize all TEAEs when each of them is considered unique, hereafter referred to as an AE count table. In addition, a listing containing individual subject AE data for all deaths and other serious and significant AEs will be provided separately. All AEs, including pre- and post-treatment AEs, will be presented in individual subject data listings.

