13.1.1.3 Documentation of Adverse Events

All AEs will be collected from the time ICF is signed until the following time points:

- For subjects who do not enroll: until time of screen failure (e.g., screen failure, withdrawal of consent)

- For enrolled subjects who have a Safety Follow-up Visit: through the Safety Follow-up Visit
- For enrolled subjects who do not have a Safety Follow-up Visit, the **latest** of:
 - 28 days after study drug treatment, or
 - The last study visit.

All subjects will be queried, using non-leading questions, about the occurrence of AEs at each study visit. When possible, a constellation of signs and/or symptoms will be identified as 1 overall event or diagnosis. All AEs for enrolled subjects will be recorded in the CRF and source document. AEs for subjects who are screened but not subsequently enrolled in the study will be recorded only in the subject's source documents. The following data will be documented for each AE:

- Description of the event
- Classification of “serious” or “nonserious”
- Date of first occurrence and date of resolution (if applicable)
- Severity
- Causal relationship to study drug(s)
- Action taken
- Outcome
- Concomitant medication or other treatment given

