9 STATISTICAL ANALYSIS

9.1 General Considerations

The Schedule of Assessments is provided in [Appendix A](#).

The precision standards for reporting safety and efficacy variables are provided in an internal Biometrics document that specifies the programming rules, including the precision for derived variables.

All individual subject data for subjects who were randomized or received study drug will be presented in individual subject data listings.

Continuous variables will be summarized using the following descriptive summary statistics: the number of subjects (n), mean, SD, standard error (SE), median, minimum value (min), and maximum value (max).

Categorical variables will be summarized using counts and percentages. Percentages will be presented to 1 decimal place unless otherwise specified.

Baseline value, unless otherwise specified, will be defined as the most recent non-missing measurement (scheduled or unscheduled) collected before administration of study drug.

Change (absolute change) from baseline will be calculated as:

Post baseline value - baseline value.

The treatment-emergent (TE) period will include the time from dosing with study drug to the Safety Follow-up Visit or 28 days after treatment / the last available visit (whichever is later) for subjects who do not have a Safety Follow-up Visit.

Unscheduled visits: Unscheduled visit measurements will be included in analysis as follows:

- In scheduled visit windows per specified visit windowing rules.
- In the derivation of baseline measurements
- In the derivation of maximum/minimum values and maximum/minimum changes from baseline values.
- In individual subject data listings as appropriate.

Visit window rules: The analysis visit windows for protocol-defined visits are provided in [Appendix B](#).

Repeated observations within the same visit window:

- For all efficacy parameters, if there are multiple measurements within a visit window, the record at the scheduled visit will be used. If there are no measurements at the scheduled visit, then 1) the record closest to the target day will be used; or 2) if there are multiple records with the same distance to the target day, the latest record will be used.
- For all safety parameters, if there are multiple measurements within a visit window, then 1) the record closest to the target day will be used; or 2) if there are multiple records with the same distance to the target day, the latest record will be used.

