9.4.1 Adverse Events

For analysis purposes, AEs will be classified as pretreatment AEs, TEAEs, or post-treatment AEs, defined as follows:

- Pretreatment AE: Any AE that started prior to dosing with study drug.
- TEAE: Any AE that developed or worsened at or after dosing of study drug through the end of the TE period.
- Post-treatment AE: Any AE that developed or worsened beyond the TE period.

For AEs with missing or partial missing start dates, if there is no clear evidence that the AEs started before or after study treatment, then the AEs will be classified as pre-treatment AEs/TEAEs/post-treatment AEs. Imputation rules for missing or partial AE start date are defined in the [Appendix D](#).

AE summary tables will be presented for TEAEs only, overall and by treatment group, and will include the following:

- All TEAEs
- TEAEs by relationship
- TEAEs by maximal severity
- Serious TEAEs

- TEAEs leading to death

Summaries will be presented by MedDRA system organ class and preferred term using frequency counts and percentages (i.e., number and percentage of subjects with an event as well as total number of events). When summarizing the number and percentage of subjects with an event, subjects with multiple occurrences of the same AE or a continuing AE will be counted once, only the maximum severity level will be presented in the severity summaries, and the worst/highest relationship level in the relationship summaries.

An AE overview table will be provided.

A listing containing individual subject AE data for all deaths and other serious AEs will be provided separately. All AEs, including pre- and post-treatment AEs, will be presented in individual subject data listings.

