Appendix D: Imputation Rules for Missing AE dates

Imputation rules for missing or partial AE start date are defined below:

If only Day of AE start date is missing:

If the AE start year and month are the same as that for the first dose date, then:

- If the full (or partial) AE end date is NOT before the first dose date or AE end date is missing, then impute the AE start day as the day of first dose date; otherwise, impute the AE start day as 1.
- Otherwise, impute the AE start day as 1.

Compare the imputed AE start date with TE period to determine whether the AE is pretreatment AE, TEAE or post-treatment AE.

If Day and Month of AE start date are missing:

If AE start year = first dose year, then:

- If the full (or partial) AE end date is NOT before the first dose date or AE end date is missing, then impute the AE start Month and Day as the Month and Day of first dose date; otherwise, impute the AE start Month as January and the Day as 1.
- Otherwise, impute the AE start MONTH as January and the DAY as 1.

Compare the imputed AE start date with TE period to determine whether the AE is pretreatment AE, TEAE or post-treatment AE.

If Year of AE start date is missing:

If the year of AE start is missing or AE start date is completely missing then query site with no imputation. Also compare the full (or partial) AE end date to the first dose date. If the AE end date is before the first dose date then the AE should be considered as a pretreatment AE. Otherwise, the AE will be considered as TEAE.

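### The SAP's longer treatment-emergent window is acceptable, but the visible SAP plans no AE tables or laboratory PCS count for the protocol's 28-day window

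*SAP*

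**What the plan says.** - Protocol 12.3.1 ends the TE period at "the Safety Follow-up Visit or 28 days after treatment for subjects who do not have a Safety Follow-up Visit".
- SAP 9.1 keeps the Safety Follow-up Visit as the end point for those who have one, and otherwise uses "28 days after treatment / the last available visit (whichever is later) for subjects who do not have a Safety Follow-up Visit".
- Protocol 8.1.4 requires the Safety Follow-up Visit "only for subjects who prematurely terminate from the study prior to Day 28 after treatment". The two definitions therefore agree for those early leavers and differ for almost everyone else.
- Protocol 13.1.1.3 collects AEs, for enrolled subjects without that visit, to the later of Day 28 and the last study visit. This is a collection rule and does not define the TE period.
- SAP 9.4 bases all safety summaries on TE-period data. Under SAP 9.4.1, "AE summary tables will be presented for TEAEs only, overall and by treatment group"; protocol 12.3.4.1 likewise says "AE summary tables will be presented for TEAEs only and will include the following". The tables are all TEAEs, by relationship, by maximal severity, serious and leading to death, with an overview. SAP 10.1.3 has the same list for the interim analysis. None is limited to the first 28 days.
- For subject counts, SAP 9.4.1 says "subjects with multiple occurrences of the same AE or a continuing AE will be counted once".
- SAP 9.4.2 counts subjects with at least one PCS laboratory event during the TE period.

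**The concern.** Safety is a primary objective, and treatment is a single dose during surgery. Protocol 8.2.2 expects drug release from the fibrin gel over several hours. The weeks after dosing are where an acute effect would be sought, and the protocol's TE definition isolates them. Under the SAP definition an event on Day 3 and one of the same term in Month 9 enter the same cell, and a subject with both counts once. A term that is more frequent in one arm early, but common in both arms later, would show a smaller difference in subject-level incidence. No visible table would recover the early figure.

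The definition also decides which laboratory draws feed the PCS counts, and whether a medication is classed as concomitant or post-treatment (SAP 9.2.3).

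**Working it through.** The plan states no figure on this point to reproduce. The check compares the two windows, then what falls in each.

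**Length of the TE period.** SAP Appendix B puts the 6-week target at Day 43 = 6 × 7 + 1, so dosing is Day 1 and elapsed days are the target minus 1. The protocol window is 28 days for a subject without a Safety Follow-up Visit.

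| Last visit | Target day | Days after dosing | Ratio to 28 |
|---|---|---|---|
| Month 3 | 91 | 90 | 3.2 |
| Month 6 | 182 | 181 | 6.5 |
| Month 12 | 365 | 364 | 13.0 |

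With the ±7-day visit allowance, a completer's window is 357 to 371 days, or 12.75 to 13.25 times 28.

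**Scheduled laboratory draws.** In protocol Table 3-1, post-dose chemistry and hematology are drawn at 24–48 hours, 6 weeks (42 days after dosing) and 3 months (90 days). For a subject who attends Month 3 and does not terminate early, the protocol window holds 1 of these and the SAP window holds 3. Scheduled post-dose ECGs (by 14 hours), coagulation tests and urinalysis (by 48 hours) lie inside both windows.

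**Dilution of an early difference (illustration; every rate is assumed).** Let p be an arm's incidence of one term in Days 0–28, and q a later incidence that is equal in both arms and independent of the early event. Full-follow-up incidence is 1 − (1 − p)(1 − q), so the arm difference is (p for VX-210 − p for placebo) × (1 − q). With p = 5% on placebo and 20% on VX-210 9 mg:

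| q | Placebo | VX-210 | Difference (points) | 95% CI half-width, 50 per arm |
|---|---|---|---|---|
| 0% | 5.0% | 20.0% | +15.0 | 12.6 |
| 10% | 14.5% | 28.0% | +13.5 | 15.8 |
| 30% | 33.5% | 44.0% | +10.5 | 19.0 |
| 50% | 52.5% | 60.0% | +7.5 | 19.4 |
| 70% | 71.5% | 76.0% | +4.5 | 17.2 |

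The half-width is 1.96 × √[p₁(1 − p₁)/50 + p₂(1 − p₂)/50], where p₁ and p₂ are the two full-follow-up incidences. A term that occurs only early (q = 0) is not diluted.

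**Partial start dates in a 28-day table.** Appendix D applies as follows when the AE end date is missing or not before dosing.
- *Only the day missing.* An onset in the dosing month takes the dose date; any other month takes its first day. If the first of a 31-day month falls on day 28 after dosing, its last day is 28 + 30 = 58 days after dosing. A true onset up to 58 days can therefore be dated into Days 0–28.
- *Day and month missing.* For the dosing year, the rule is to "impute the AE start Month and Day as the Month and Day of first dose date"; another year takes 1 January. Dosing on 1 January with onset on 31 December is 364 days, dated to dosing. Dosing on 4 December puts 1 January at day 28, so onset on the following 31 December (27 + 365 = 392 days) would also be dated into the window. Depending on the dosing date, the true onset can thus be at any time in follow-up.
- *Direction.* Imputation can only bring late onsets into Days 0–28. It moves no early onset out.

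Enumerating 365 dosing dates in a non-leap year, with late onsets spread evenly (an assumption), the share of late onsets dated into Days 0–28 is:

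| True onset, days after dosing | Day missing | Day and month missing |
|---|---|---|
| 29–364 | 4.4% | 53.8% |
| 29–181 | 9.6% | 78.9% |
| 29–90 | 23.7% | 91.4% |

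These are shares of partially dated late AEs. How many such AEs there will be is unknown.

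**The case against.** The strongest reply is that this is a benign difference. The SAP window matches the protocol's own collection rule, adds later events to the tables and drops none. Protocol section 12 leaves statistical detail to the SAP. That stands, and it is why the window should be kept.

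Several features also soften the loss. SAP 9.4.1 reports total numbers of events as well as subjects, and gives separate relationship and serious TEAE tables. Laboratory values are summarized by time point, so only the PCS count pools draws. All AEs are listed. The IDMC reviews safety under a separate SAP that was not available. None of these gives a planned 28-day incidence by arm in the visible final analysis, but they limit what is lost.

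The dilution table rests wholly on assumed rates. From q = 10% upward its differences are smaller than their half-widths, so imprecision matters as well as dilution. The partial-date problem arises mainly once an early table is added; under the SAP window most of these AEs are treatment-emergent whichever day is imputed.

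A reader might infer that the SAP conceals early safety data or that a real signal will be missed. The documents support neither: the events stay in the tables and listings, and no AE rates are given. Nor can it be said that the departure is unexplained throughout the SAP. Its contents list runs from section 2 to section 4, and some text is redacted.

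**Conclusion.** The two definitions differ for nearly all subjects who remain past Day 28, and the visible SAP leaves out the AE tables that the protocol's definition would produce. What follows from the documents alone is a 28-day window against about 364 days for a completer, and 1 scheduled post-dose chemistry/hematology draw against 3 in the PCS count. The size of any dilution is unknown; the illustration shows only its form, a factor of 1 − q, under equal and independent late incidence.

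This is a cheap improvement of low priority. A reader might go further and call the SAP window an error, or hold that it needs a protocol amendment or invalidates the safety analysis. The collection rule in protocol 13.1.1.3 and the deferral of detail to the SAP in protocol section 12 speak against that.

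**What to change.** Keep the SAP 9.1 window, and make these changes before final database lock and unblinding, as SAP section 4 allows:

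- **SAP 9.4.1:** prespecify the existing AE tables a second time (overview, all TEAEs by SOC and PT, relationship, maximal severity, serious, leading to death) for the protocol window: dosing to the Safety Follow-up Visit, or to Day 28 if there is none.
- **SAP 9.4.2:** give the chemistry and hematology PCS count for the same window.
- **Partial dates:** place AEs by the Appendix D date, and include those with no start year that Appendix D already treats as TEAEs. Footnote by arm the number with imputed or missing start dates, and add a count excluding them.

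A sentence in SAP 9.1 noting the departure from protocol 12.3.1 would be tidy if text not shown lacks it, but it is documentation only. No new data and no protocol amendment are needed. The cost is a rerun of existing programs and one more set of descriptive tables to produce and read.

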9.2 Background Characteristics

9.2.1 Subject Disposition

The number of subjects in the following categories will be summarized overall and by treatment group based on the All Subjects Set:

- All Subjects Set
- Randomized
- Dosed (Safety Set)
- Full Analysis Set (FAS)

The number and percentage (based on the Full Analysis Set) of subjects in each of the following disposition categories will be summarized overall and by treatment group:

- 6-Month Follow-up Visit Occurred
- Completed study
- Prematurely discontinued the study and the reasons for discontinuation

A listing will be provided for disposition, including the subjects who discontinued study with reasons for discontinuation. A randomization listing will be provided with subjects ordered by randomization date. A summary table for the randomization by stratification factors and by site will also be provided.

9.2.2 Demographics and Baseline Characteristics

Demographics and baseline characteristics will be summarized overall and by treatment group based on the Full Analysis Set.

Demographic data will include the following:

- Sex (female and male)
- Age at baseline (in years)
- Age group (<30 versus ≥30 years of age)
- Ethnicity (Hispanic or Latino, not Hispanic or Latino, and not collected per local regulations)
- Race (White, Black or African American, Asian, American Indian or Alaska Native, Native Hawaiian or Other Pacific Islander, not collected per local regulations, and Other)
- Country

Baseline characteristics will include the following:

- Weight (kg)
- Height (cm)
- BMI (kg/m²)
- AIS Grade (A or B with or B without sacral pinprick preservation)
- Baseline UEMS score (total, left and right)

All medical history will be coded using the latest version of Medical Dictionary for Regulatory Activities (MedDRA). Medical history will be summarized using descriptive statistics by MedDRA system organ class (SOC) and preferred term (PT). Medical history will also be displayed in a subject listing.

9.2.3 Prior and Concomitant Medications

Medications used in this study will be coded by using the World Health Organization Drug Dictionary Enhanced (WHODDE) and categorized as follows:

Prior medication: any medication that started before the dose date of study drug, regardless of when the medication ended.

Concomitant medication: medication continued or newly received on or after the dose date of study drug through the end of the TE period.

Post-treatment medication: medication continued or newly received after the TE period.

A given medication may be classified as follows: prior, concomitant, post-treatment, both prior and concomitant, both concomitant and post-treatment, or prior, concomitant, and post-treatment.

If a medication has a completely missing or partially missing start/stop date and it cannot be determined whether it was taken before the dose date, concomitantly, or after the TE period, it will be classified as prior, concomitant, and post-treatment. Imputation rules for missing or partial medication start/stop dates are defined in [Appendix C](#).

Prior medications and concomitant medications will be summarized descriptively by (1) preferred names; (2) anatomic class (ATC) level 1, ATC level 2, and preferred names based on the Full Analysis Set.

Summaries of medications will be based on the Full Analysis Set.

Post-treatment medications will be listed by subject.

9.2.4 Study Drug Exposure

Study drug exposure will be presented in an individual data listing to indicate whether the study drug was administered.

9.2.5 Study Drug Compliance

Not applicable.

9.2.6 Important Protocol Deviations

An important protocol deviation (IPD) is a deviation that may significantly affect the completeness, accuracy, or reliability of the study data or that may significantly affect a subject's rights, safety, or well-being. IPDs will be identified from the clinical database and/or site deviation log, and finalized prior to the database lock.

The protocol deviations that should be considered as potential IPDs may fall in, but are not limited to, the following categories:

- Safety
- Informed consent
- Eligibility and entry criteria
- Randomization
- Investigational medicinal product
- Study procedures and laboratory assessments

The protocol deviations that fall in these categories are categorized as IPDs only if they have the potential to significantly affect the completeness, accuracy, or reliability of the study data or to significantly affect a subject's rights, safety, or well-being.

IPDs will be provided in an individual subject data listing.

